2.3.1. Risks for Study Participation

All therapies have the potential to cause adverse experiences. To date, clinical data with JNJ-64281802 are available from the Phase 1 FIH study DNG1001, study DNG1004, study DNG1005, and study DNG1006, in healthy adult participants. JNJ-64281802 was generally well tolerated, and no safety concerns were identified at single doses up to 1,200 mg and at multiple doses up to 560 mg once daily for 10 days, 400 mg once daily for 31 days, or 800 mg twice daily for 2 days.

Potential Risks of Clinical Significance	Summary of Data/ Rationale for Risk	Mitigation Strategy	
Risks Due to Study Intervention			
Reproductive risks and pregnancy	Animal studies with JNJ-64281802 did not indicate harmful effects with respect to reproductive toxicity. There were no test article-related effects on embryo-fetal development in pregnant rats up to 500 mg/kg/day and in pregnant rabbits up to 180 mg/kg/day, which were the highest dose levels tested. Excessive maternal toxicity was evident at 180 mg/kg/day in rabbits. The effect of JNJ-64281802 on sperm, on conception, or on a fetus or nursing baby is unknown. In addition, no drug-drug interaction studies have been performed and hence the potential effect of JNJ-64281802 on contraceptive efficacy of hormonal contraceptives is unknown.	Refer to Inclusion Criteria 6, 7, 8 and Exclusion Criterion 14 for women, and Inclusion Criteria 9 and 10 and Exclusion Criterion 15 for men in this study.	
Rash	In study DNG1001, 2 Grade 2 events of rash occurred in the multiple ascending dose part (N=47) that were considered very likely related to JNJ-64281802 by the investigator. Both events were resolved after 35 to 47 days. A causal relationship between the events of rash and the study intervention cannot be excluded.	Additional safety follow-up procedures will apply, as described in the rash management protocol in Appendix 2: Rash Management.	

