7.1.3. Study Pausing Criteria

If significant safety concerns arise following administration of study intervention (and a specific set of study pausing criteria have been met), further randomization and dosing of participants may be paused.

The reasons for pausing the study are listed below. The list only applies for events that are considered by the investigator to be related to study intervention and unrelated to dengue disease or an associated infection (eg, COVID-19).

- Death of a participant, considered related to study intervention or if the causal relationship to the study intervention cannot be excluded; OR
- Three or more participants at one study site or six or more participants at all study sites experience a ≥Grade 3 unsolicited AE of the same type (as per medical judgment of the sponsor) that is considered related to study intervention;

Note: An AE report based on a \geq Grade 3 laboratory abnormality will only be considered if the laboratory abnormality is clinically significant and persistent (upon repeated testing) per the investigator. Elevations of total cholesterol will not be considered.

OR

• Any safety findings that in the opinion of the sponsor or the IDMC warrants pausing (or cessation) of dosing.

To enable a prompt response to a situation that could trigger the study pausing criteria, the investigator should notify the sponsor's medical monitor (or designee) immediately and no later than 24 hours after becoming aware of any ≥Grade 3 unsolicited AE considered related to study intervention (and update the CRF with relevant information on the same day the AE information is collected). A thorough analysis of all reported ≥Grade 3 unsolicited AEs will initially be carried out by the sponsor's medical monitor (or designee). Based on the available data, the sponsor's medical monitor (or designee) will determine whether a safety data review by the IDMC is warranted, to assess whether the study pausing criteria are met.

If the IDMC judges that the study pausing criteria have been met, the IDMC will recommend to either pause the study or to implement modifications to the study conduct and/or to the safety assessments. If safety concerns would occur only with the HDR, the IDMC may recommend to pause randomization and dosing in the HDR group but continue randomization and dosing in the LDR and placebo groups.

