8.3. Adverse Events, Serious Adverse Events, and Other Safety Reporting

Timely, accurate, and complete reporting and analysis of safety information, including AEs, SAEs, and product quality complaint (PQC), from clinical studies are crucial for the protection of participants, investigators, and the sponsor, and are mandated by regulatory agencies worldwide. The sponsor has established Standard Operating Procedures in conformity with regulatory requirements worldwide to ensure appropriate reporting of safety information; all clinical studies conducted by the sponsor or its affiliates will be conducted in accordance with those procedures.

Adverse events will be reported by the participant (or, when appropriate, by a caregiver, surrogate, or the participant's legally acceptable representative) for the duration of the study. Adverse events and concomitant medication will be recorded by the participant in a diary, except in case of discontinuation of study intervention or study (see Section 1.3.2.4) where they will be collected by study site personnel.

For further details on AEs, SAEs, and PQC refer to Appendix 7: Adverse Events, Serious Adverse Events, Product Quality Complaints, and Other Safety Reporting: Definitions and Procedures for Recording, Evaluating, Follow-up, and Reporting.

8.3.1. Time Period and Frequency for Collecting Adverse Event and Serious Adverse Event Information

All Adverse Events

All AEs and special reporting situations, whether serious or non-serious, will be reported from the time a signed and dated ICF is obtained until completion of the participant's last study-related procedure, which may include contact for follow-up of safety, or until the participant has been deemed lost to follow-up after demonstration of due diligence of follow-up efforts.

For any ≥Grade 3 unsolicited AE, whether serious or non-serious, the investigator will as soon as possible assess the possible relationship to study intervention. If the investigator considers the ≥Grade 3 unsolicited AE to be related to study intervention, the investigator will notify the sponsor's medical monitor (or designee) immediately and no later than 24 hours after becoming aware of the AE.

Serious Adverse Events

All SAEs occurring during the study must be reported to the appropriate sponsor contact person by study site personnel immediately, but no later than 24 hours of their knowledge of the event.

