8.3.2. Method of Detecting Adverse Events and Serious Adverse Events

Care will be taken not to introduce bias when detecting AEs or SAEs. Open-ended and nonleading verbal questioning of the participant is the preferred method to inquire about AE occurrence.

Solicited Adverse Events

Solicited AEs are predefined events for which the participant is specifically questioned. Signs and symptoms of DENV infection (DENV-infection associated AEs) will be collected by the investigator or designee as solicited AEs (Table 3). DENV-associated signs and symptoms (systemic solicited AEs) will be recorded daily by the participant in a diary. In case a particular systemic solicited AE was not observed at time of recording but occurs later that day, the participant should record this. In case the systemic solicited AE is fever, oral body temperature should also be recorded. For oral measurement of body temperature at home to assess fever, participants will be provided with a thermometer.

All AEs are evaluated using the gradings presented in Table 4, the modified DAIDS Table for Grading the Severity of Adult and Pediatric Adverse Events supplemented with WHO toxicity grading scales in Section 10.9, or the rash management protocol in Section 10.2.

Table 3: Solicited Adverse Events

Systemic Reactogenicity

- Retro-orbital pain a
- Abdominal pain a
- Arthralgia a
- Fever b
- Headache b
- Nausea b
- Fatigue b
- Myalgia b
- Loss of appetite a
- Vomiting b
- Diarrhea b
- Rash c
- a. Grading according to Table 4.
- b. Grading according to the modified DAIDS Table for Grading the Severity of Adult and Pediatric Adverse Events supplemented with WHO toxicity grading scales in Section 10.9.
- c. Grading according to the rash management protocol in Section 10.2.

Table 4: Grading of Solicited Adverse Events

Reaction to Intervention	Mild (Grade 1)	Moderate (Grade 2)	Severe (Grade 3)	Potentially Life- threatening (Grade 4)
Retro-orbital pain, Arthralgia, Abdominal pain	Event that is easily tolerated, may require 1 dose of medication/treatment	Event that interferes with daily activity or requires > 1 dose of medication/treatment	Event that prevents daily activity	Life-threatening

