Loss of appetite	Loss of appetite without alteration in eating habits	Oral intake altered without significant weight loss or malnutrition; oral nutritional supplements indicated	Associated with significant weight loss or malnutrition (eg inadequate oral caloric intake and/or fluid intake); tube feeding or total parenteral nutrition indicated	Life-threatening consequences; urgent intervention indicated

Unsolicited Adverse Events

Unsolicited AEs are all AEs for which the participant is not specifically questioned.

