10.2. Appendix 2: Rash Management

Dengue symptomatic infection is known to result in skin rashes in most patients. Rashes may potentially also be related to the study intervention, and it may not be possible to differentiate between a rash secondary to DENV infection and one related to the study intervention. In all cases of rash that are not related to DENV infection, the below rash management should be followed.

In case a causal relationship between the rash and the study intervention cannot be excluded, then the following visits and assessments will be performed as indicated. Unscheduled follow-up visits for close follow-up of rash will be performed based on the grade (severity) of the rash. At the investigator's discretion, additional visits and assessments can be performed.

If a causal relationship between the rash and the study intervention cannot be excluded, safety blood samples need to be taken during the (unscheduled) visits as described below. The following parameters need to be tested: aspartate aminotransferase (AST), ALT, creatinine, erythrocyte sedimentation rate, and a complete blood cell count (including hemoglobin, hematocrit, red blood cell [RBC] count, white blood cell [WBC] count, neutrophils, lymphocytes, monocytes, eosinophils, basophils, and platelet count).

The rash event should be captured in the Adverse Event Section of the CRF, and in more detail in the specific rash assessment pages of the CRF.

Participants should be informed that they should contact the investigator and visit the study site immediately (unscheduled visit, Day 0 of the rash) when they notice any rash. The skin reaction should be evaluated at the study site the same day (if possible) or the next day. Participants should be advised to contact the investigator immediately if there is any worsening of the rash, if any systemic signs or symptoms appear, or if mucosal involvement develops.

Grading of rash events will be based on the Division of Acquired Immunodeficiency Syndrome (DAIDS) Table for Grading the Severity of Adult and Pediatric Adverse Events (DAIDS 2017).

Monitoring of the evolution of rash events will be performed as described in Table 5 below.

 Table 5:
 Management of Rash Events by Severity Grade

Status: Approved, Date: 19 July 2023

			•	
	Definition	Study	Activities by Day ^a	Referral to Dermatologist
		Intervention		and Dermatology
		Action		Activities

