10.11.2. Follow-up Assessments

- **Repeat testing** to confirm laboratory abnormalities within 24 hours prior to stopping, unless safety is considered at risk by the sponsor and/or investigator
- Report the event to the sponsor within 24 hours to decide on discontinuing study intervention

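### Does limiting the numeric pausing rule and the 24-hour notice to unsolicited adverse events leave drug-related Grade 3 rash without oversight?

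*Protocol*

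**What the plan says.** Section 7.1.3 of the protocol has three pausing criteria: a death related, or possibly related, to study intervention; a count of three participants at one site or six across sites who "experience a ≥Grade 3 unsolicited AE of the same type (as per medical judgment of the sponsor) that is considered related to study intervention"; and any safety finding that the sponsor or the Independent Data Monitoring Committee (IDMC) thinks warrants a pause. The list as a whole is confined to events that the investigator judges drug-related and not due to dengue or an associated infection.

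Section 8.3.1 sets the expedited notice in the same terms: "If the investigator considers the ≥Grade 3 unsolicited AE to be related to study intervention, the investigator will notify" the medical monitor within 24 hours. Section 8.3.2 draws the dividing line: "Unsolicited AEs are all AEs for which the participant is not specifically questioned", while "Signs and symptoms of DENV infection (DENV-infection associated AEs) will be collected by the investigator or designee as solicited AEs". Rash is one of the 12 solicited events in Table 3, with the footnote "Grading according to the rash management protocol in Section 10.2". Section 10.2 then states: "In all cases of rash that are not related to DENV infection, the below rash management should be followed".

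**The concern.** Rash is the drug reaction that the protocol itself singles out. Section 2.3.1 reports that "2 Grade 2 events of rash occurred in the multiple ascending dose part (N=47) that were considered very likely related to JNJ-64281802". Yet solicited status depends on whether participants are asked about an event, not on its cause, so a rash judged drug-related and unrelated to dengue stays solicited. It is then outside the only pausing criterion with a number in it, and outside the 24-hour notice. The rash plan in Section 10.2 states no timed report to the sponsor, whereas the liver plan does: "Report the event to the sponsor within 24 hours to decide on discontinuing study intervention". If this were an oversight, a cluster of non-serious Grade 3 rashes across sites could build up with no fixed count and no clock obliging anyone to look at them together.

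**Working it through.** The documents state no operating characteristic for the pausing rule, so there is no figure to reproduce. The check is mainly textual.

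**1. Does the wording conflict anywhere?** The restriction to unsolicited events of Grade 3 or higher appears in:

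- Section 7.1.3: the numeric criterion, the 24-hour notice, the medical monitor's analysis, and the IDMC's follow-up after a numeric trigger (four places);
- Section 8.3.1: the causality assessment and notice;
- Section 10.6.6: the matching IDMC trigger.

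That is six places with the same limit. The change log for Amendment 2 (Section 10.12) uses the same term and records that the pausing criteria were added at a health authority's request. That does not show that the authority chose the term, but uniform use points to deliberate drafting. Sections 8.3.2 and 10.2 define and manage rash; neither says that it counts toward the numeric criterion. Nothing contradicts anything else.

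**2. What falls outside?** One of three pausing criteria, for all 12 Table 3 event types, when the event is Grade 3 or higher, drug-related, unrelated to dengue and non-serious. Serious rash goes through 24-hour SAE reporting, and a related death is a criterion by itself.

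**3. What still applies to such a rash?**

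- Section 10.2, Table 5: permanent discontinuation at Grade 3, dermatology referral, and biopsy and photographs within 24 hours of onset. The photographs go to a sponsor server that sponsor team and IDMC members can open.
- Section 7.1.3: the any-safety-finding criterion, which does not mention solicited or unsolicited status.
- Section 10.6.6: IDMC review of unblinded data after a significant or unexpected safety event, plus regular safety checks.
- SAP Sections 5.6.2 and 5.7.4: the regular IDMC analyses include adverse events, with solicited and unsolicited events in separate tables and summaries by toxicity grade and by relationship, per intervention group.

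**4. Is there a reason for the narrower scope?** Section 10.2 says that a dengue rash and a drug rash may not be distinguishable. Section 6.3 allows virologic data to be kept from investigators. A count that relies on the investigator's view that a dengue-like symptom is not dengue would therefore be hard to apply, whereas the IDMC sees the arms unblinded.

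**5. Scale.** Planned enrolment is 1,250 to 1,850 at 1:1:1.

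- Active-arm participants: 2/3 × 1,250 = 833; 2/3 × 1,850 = 1,233.
- Threshold of six as a share: 6/833 = 0.72%; 6/1,233 = 0.49%. If only half were on active drug: 1/2 × 1,250 = 625 and 6/625 = 0.96%.
- Phase 1 rash: 2/47 = 4.3%, both Grade 2. No Grade 3 rate is given.

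As written, non-serious solicited rash adds 0 to the count at any rate. Had it counted, the chance of reaching six would be P(X ≥ 6) = 1 − Σ(k = 0 to 5) C(N,k) pᵏ(1 − p)ᴺ⁻ᵏ, with p assumed:

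| Assumed Grade 3 rash rate p | N = 833 | N = 1,233 |
|---|---|---|
| 0.25% | 0.02 | 0.09 |
| 0.5% | 0.24 | 0.58 |
| 1% | 0.84 | 0.98 |
| 2% | >0.99 | >0.99 |

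The answer runs from almost never to almost always over a range that the documents do nothing to narrow. The arithmetic cannot show that a pause would be missed.

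**The case for a change.** The strongest counter-argument is that Section 7.1.3 already removes events judged to be dengue, so the word unsolicited takes out only events that the investigator has already called drug-related. Grade 3 rash need not be serious: a diffuse rash with vesicles qualifies without hospitalization. The liver route does not fill the gap, because its criteria start at three times the upper limit of normal and rash without liver change is not covered. Every remaining route for non-serious rash depends on someone's judgment or on a meeting date.

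The factual part stands: there is no fixed count and no 24-hour clock for this event. The inference is weaker.

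- The dengue filter is only as good as the investigator's ability to separate the two causes, which Section 10.2 doubts.
- The numeric route also rests on judgment: causality by the investigator, sameness of type by the sponsor, the monitor's decision to involve the IDMC, and the IDMC's own finding. Even then a pause is optional.
- The liver comparison does not carry over. That report serves a joint decision on whether to stop dosing; Grade 3 rash already requires stopping, and the liver plan states no link to the pausing rule either.

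**Conclusion.** The concern does not hold. The scope is narrow by wording that is uniform across the protocol, it has a reason that the protocol's own text supports, and drug-related Grade 3 rash remains visible to the sponsor and to the unblinded IDMC. What is left is one of three pausing criteria, for non-serious related events only. Asking the sections to agree would achieve nothing, since they already do, and restating the present exclusion would satisfy the request. Widening the trigger would be a different clinical rule with its own costs, such as reviews of rashes that cannot be told from dengue; this note takes no position on it.

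No efficacy or safety analysis in the SAP depends on the point. According to SAP Section 1, the study ended on 02 October 2024 for portfolio reasons and not because of a safety concern, so a change to the pausing rule would now have little left to act on.

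The conclusion assumes that the IDMC reviews took place as SAP Section 5.7.4 describes. The IDMC charter was not available and may say more about rash.

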7.2. Participant Discontinuation/Withdrawal From the Study

A participant will be withdrawn from the study for any of the following reasons:

- Lost to follow-up
- Withdrawal of consent
- Death
- Failure to comply with the protocol requirements or to cooperate with the study site personnel

When a participant withdraws before study completion, the reason for withdrawal is to be documented in the CRF and in the source document.

For participants who discontinue the study prematurely for reasons other than withdrawal of consent, a withdrawal visit and a follow-up will be performed (see Section 7.1, Discontinuation of Study Intervention and Section 1.3.2.4, Discontinuation From Study Intervention or Study).

HHCs who withdraw consent from the study will be offered a follow-up visit. Index cases who withdraw consent/assent during screening (ie, their only visit in the study) will not be followed up.

Withdrawal of Consent/Assent

A participant declining to return for scheduled visits does not necessarily constitute withdrawal of consent. Alternate follow-up mechanisms that the participant agreed to when signing the consent form apply (eg, consult with family members, contacting the participant's other physicians, medical records, database searches, use of locator agencies at study completion) as local regulations permit.

7.2.1. Withdrawal From the Use of Research Samples

A participant who withdraws from the study will have the following options regarding the optional research samples (only applicable to pharmacogenomic research samples; see Section 8.5):

- The collected samples will be retained and used in accordance with the participant's original separate informed consent for optional research samples.
- The participant may withdraw consent for the optional research samples, ie, samples for pharmacogenomic analysis, in which case, the samples will be destroyed, and no further testing will take place. To initiate the sample destruction process, the investigator must notify the sponsor study site contact of withdrawal of consent for the optional research samples and to request sample destruction. The sponsor study site contact will, in turn, contact the biomarker representative to execute sample destruction. If requested, the investigator will receive written confirmation from the sponsor that the samples have been destroyed.

Withdrawal From the Optional Research Samples While Remaining in the Main Study

The participant may withdraw consent for the optional pharmacogenomic research samples while remaining in the study. In such a case, the optional research samples will be destroyed. The sample destruction process will proceed as described above.

Withdrawal From the Use of Samples in Future Research While Remaining in the Main Study

The participant may withdraw consent for use of samples for additional future research (refer Section 10.6.5, Long-term Retention of Samples for Additional Future Research). In such a case, samples will be destroyed after they are no longer needed for the clinical study. Details of the sample retention for research are presented in the main ICF and in the separate ICF for the optional pharmacogenomics research samples.

7.3. Lost to Follow-up

To reduce the chances of a participant being deemed lost to follow-up, prior to randomization attempts should be made to obtain contact information from each participant, eg, home, work, and mobile telephone numbers and email addresses for both the participant as well as appropriate family members.

A participant will be considered lost to follow-up if the participant repeatedly fails to return for scheduled visits and is unable to be contacted by the study site. A participant cannot be deemed lost to follow-up until all reasonable efforts made by the study site personnel to contact the participant are deemed futile. The following actions must be taken if a participant fails to return to the study site for a required study visit:

- The study site personnel must attempt to contact the participant to reschedule the missed visit as soon as possible, to counsel the participant on the importance of maintaining the assigned visit schedule, to ascertain whether the participant wishes to or should continue in the study.
- Before a participant is deemed lost to follow-up, the investigator or designee must make every reasonable effort to regain contact with the participant (where possible, 3 telephone calls, e-mails, fax, and, if necessary, a certified letter to the participant's last known mailing address, or local equivalent methods), and to determine the reason for discontinuation/withdrawal. These contact attempts should be documented in the participant's medical records.
- Should the participant continue to be unreachable, they will be considered to have withdrawn from the study.

Should a study site close, eg, for operational, financial, or other reasons, and the investigator cannot reach the participant to inform them, their contact information will be transferred to another study site.

